PET data will be acquired in listmode and subsequently used for simulation to determine the potentially lowest dose feasible using the next generation digital PET/CT technology.

Recruitment

Potential participants will be identified through brochures, contact with vape shops, and social media postings. Brochures will be distributed at vape shops, and social media postings will be made in interest groups. A link to an informational video will also be provided in the brochure. To determine eligibility, participants will sequentially complete two eligibility surveys.

Version: December 20, 2017 Page 3 of 16

Survey 1

The brochures and social media postings will include a link to Eligibility Survey 1. Survey 1 will collect sensitive, medical information, but will be completely anonymous. Medical information will be collected solely for the purposes of determining participant eligibility and will be unlinked from any identifying participant information as well as future collected study data.

Survey 2

Once participants are determined eligible by Survey 1, they will be directed to complete Survey 2 to confirm their eligibility. Survey 2 will ask participants questions about their vaping habits. If they are confirmed eligible from the survey, they will also be asked to provide their name and contact information (e-mail). Study personnel will then contact eligible participants to schedule a time for them to come to the WCIBMI for their initial visit. Responses from Survey 1 and Survey 2 will be completely unlinked to maintain anonymity about participants' medical information.

Selection Criteria

Inclusion Criteria

- Males and females of 18 years of age or older
- Current regular user of e-cigarettes (use at least once daily for the past 30 days) with nicotine strength > 6 mg/ml.
- Healthy medical history
- Abstinent from any tobacco/nicotine use for 4 hours prior to imaging

Exclusion Criteria

- Not a regular user of e-cigarettes
- Pregnant or lactating (only excluded from imaging study)
- Prisoner
- Incapable of giving informed consent
- Being claustrophobic
- Unable to lie flat on the scanner for extended periods of time
- Unstable medical condition such as heart disease, uncontrolled hypertension, thyroid disease, diabetes, renal or liver impairment, or glaucoma
- Prostatic hypertrophy, stroke, ulcer in the past year
- Psychiatric conditions such as schizophrenia, adult ADHD, or bipolar disorder

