For those subjects that have indicated their interest to participate in the imaging study, the following additional steps will occur during the dress rehearsal visit:

- Participants will be informed about the further study details, the consent form will be reviewed and signed, and an imaging date will be scheduled.
- Participants will be given the e-cigarette that will be used in the study so that they can get accommodated to the device and practice vaping in the supine position.
- For female subjects participating in the imaging procedure, urine will collected during the screening visit to confirm that they are not pregnant.

All subjects participating in the imaging study will be required to have a full dress rehearsal at the WCIBMI prior to their imaging procedures in order to practice and be familiar with the study facilities/procedure: the gowning into hospital scrubs and protective gear, the proper posture for PET scanning, and the e- cigarette vaping and exhaling procedure. There will be no PET/CT imaging or ¹¹C-nicotine radiation exposure during the dress rehearsal.

Subjects who initially agree only to the dress rehearsal are eligible to add the subsequent imaging study without an additional dress rehearsal unless requested by the PI. The subject will complete appropriate consent documentation of their expanded participation. The dress rehearsal and subsequent ¹¹C-nicotine PET/CT imaging examination will follow the same steps.

Subject Gowning

The subject will wear hospital scrubs and personal protective gear in order to minimize any ¹¹C radioactive deposits from the exhaled vape. The subject will also wear two sets of gloves. The gowning will be guided and monitored by research project personnel.

Figure: Subject gowning procedure. Still pictures from a training video demonstrate the subject gowning procedure with personal protective gear.

Version: December 20, 2017 Page 8 of 16

Subject Positioning on the PET/CT System

After gowning, the subject will be placed on the PET/CT system. A knee support pad and a head-holder will be available and used to improve subject comfort and minimize subject motion.

Once the subject is comfortably positioned, the surview scan will be performed using CT only, and the PET/CT imaging field will be planned. Once the imaging field is determined, an attenuation CT scan of the imaging field will be acquired.

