The e-cigarette will be brought to the PET/CT suite in a transport box. Once all preparations are completed for the PET image acquisition, the subject will be given the e-cigarette.

Figure: Subject positioning procedure. These still pictures from a training video demonstrate the subject positioning procedure on the PET/CT system, including the process of handing over the e-cigarette (lower center), and the process for the subject to hold the e-cig during vaping (lower right).

E-cigarette Vaping

The following figure presents still pictures from the training video to demonstrate the handover of the e-cig to the subject, how the subject should handle the e-cig, and the process of vaping as instructed with up to 10 puffs.

Version: December 20, 2017 Page 9 of 16

Figure: ¹¹C-nicotine e-cigarette puffing procedure. Still pictures from a training video demonstrate the handling of the c-cig in the PET/CT system, the handover to the subject, handling of the e-cigarette during vaping, and return of the device to staff.

Subject De-gowning

The following figure presents still pictures from the training video to demonstrate the de-gowning procedure of the participant.

Figure: Subject de-gowning procedure. Still pictures from a training video demonstrate the participant de-gowning procedure. The participant will remove and dispose of all personal protective gear, and study personnel will subsequently evaluate the radiation levels of the participant.

Imaging Visit

All subjects will be contacted 24-48 hours prior to the imaging study to confirm their availability and continued participation. The procedures detailed for the dress rehearsal will also be followed for the imaging session. The subject will again disrobe and change into hospital scrubs. The subject

Version: December 20, 2017 Page **10** of **16**

will wear full-body disposable personal protective equipment (PPE) including a gown, hairnet, double latex gloves, and foot coverings.

The subject will be positioned on the PET/CT during the transport of the ¹¹C- e-cig material from Kinnear to the WCIBMI (15 minutes prior to study of vaping).

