Once the ¹¹C-nicotine e-cigarette enters the PET/CT facility, it will be placed into the facility's dose calibrator for a secondary dose confirmation and then transported directly to the PET/CT imaging room. The subject will then be instructed to start inhalation (maximum 10 puffs at 30 second intervals) while positioned in the PET/CT system. Afterwards, the used e-cigarette will be removed from the imaging system by a staff member, and its remaining residual ¹¹C-nicotine activity determined using a dose calibrator.

PET imaging will be performed for a maximum of 60 minutes following onset of ¹¹C-nicotine inhalation/vaping. After PET imaging is completed, the subject will be de-gowned, and the radiation levels will be determined. The subject will be asked to stay in the patient waiting/recovery area for up to 120 minutes (2 hours). Prior to release, the subject will be surveyed again to ensure that any exhaled breath/air is at background radioactivity levels. Additionally, all subjects will be contacted within 24 – 48 hours after release from the study to ensure that they are feeling well and have not experienced any adverse reaction to the study. Any adverse reactions will be recorded and reported immediately to the PI.

The medical records for the subjects will not be obtained for this study. Participants will be asked to provide medical information in an eligibility survey only to confirm their eligibility. Responses to this survey will be entirely anonymous and confidential. In addition, there will be no personal data recorded other than the subject's gender, age, ethnicity, weight, height, and length of time that they have been smoking and/or using e-cigarettes. All subject data will use coded identifiers in all imaging files with subject numbers replacing the typically patient name fields.

Imaging

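### The Imaging Visit section fixes latex as the glove material, but no criterion or visit step covers latex allergy, so an allergic participant could be exposed

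*Protocol*

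**What the plan says.** The Imaging Visit section of the protocol states that the subject "will wear full-body disposable personal protective equipment (PPE) including a gown, hairnet, double latex gloves, and foot coverings". It applies to every imaging subject and gives no alternative.

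The Subject Gowning section covers the same step without naming a material: "The subject will also wear two sets of gloves". It gives the purpose of the protective gear as limiting radioactive deposits from exhaled aerosol, and it has project staff guide and watch the gowning. The Imaging Visit section ties the two visits together: "The procedures detailed for the dress rehearsal will also be followed for the imaging session".

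On medical screening, the nearest inclusion criterion is "Healthy medical history". The nearest exclusion is "Unstable medical condition such as heart disease, uncontrolled hypertension, thyroid disease, diabetes, renal or liver impairment, or glaucoma".

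On sources of medical information, the Imaging Visit section says "The medical records for the subjects will not be obtained for this study" and "Participants will be asked to provide medical information in an eligibility survey only to confirm their eligibility". For Survey 1, the Recruitment section says: "Medical information will be collected solely for the purposes of determining participant eligibility and will be unlinked from any identifying participant information".

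**The concern.** The protocol makes a definite choice of material for something worn against the skin, and it provides no written way to find the people for whom that material is a problem. Latex allergy is compatible with otherwise good health, so a general requirement for a healthy history does not identify it. Participants are volunteers who, by the protocol's own statement, gain no direct benefit. An avoidable exposure is therefore hard to justify, however small the risk. What is at stake is participant safety. No objective, endpoint, comparison or sample-size argument depends on the gloves.

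**Working it through.** The plan states no figure on this point, so there is none to reproduce. The check is a reading of each place where latex allergy could be picked up before the gloves go on.

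1. **Selection Criteria.** The lists name specific diseases, psychiatric conditions, medications, claustrophobia and inability to lie flat. Neither latex nor allergy of any kind appears.
2. **Survey 1 (Recruitment).** Its items are not shown, so it may contain an allergy question. Even then, no listed criterion would exclude on the answer. The answers are also detached from identity, so gowning staff cannot look them up.
3. **Survey 2 (Recruitment).** It asks about vaping habits and, for those eligible, takes contact details.
4. **Screening Visit – Dress Rehearsal.** The steps described include a check for claustrophobia, a pregnancy test for women who will be imaged, practice with the device, and gowning. There is no allergy question.
5. **Contact 24 to 48 hours before imaging.** It serves only to check that the subject is still available and willing.
6. **Imaging Visit.** No question is asked before gowning. Medical records are not obtained, and the personal data recorded are limited to a short list of demographic, body-size and smoking or vaping items.
7. **Risks.** Radiation, the moving table and inconvenience are covered. Latex is not mentioned.
8. **Contact 24 to 48 hours after release.** It asks about adverse reactions, but this comes after any exposure.

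No written step closes the gap.

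**Is latex needed for anything stated?** Set side by side, Subject Gowning asks for two sets of gloves and Imaging Visit asks for two sets of latex gloves. The first gives the purpose of the gear and the second adds the material. No sentence gives a reason for latex.

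**Size.** The Participant Procedures section sets a maximum of 30 imaging subjects. The documents give no allergy prevalence, so a range of 1% to 4% is assumed:

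- lower end: 30 × 0.01 = 0.3 subjects
- upper end: 30 × 0.04 = 1.2 subjects

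These are upper bounds at each assumed prevalence. They suppose that nobody is screened out, nobody discloses the allergy and nobody is asked. They count allergic people who could be gloved in latex, not reactions. One repeat session per subject is allowed, so there could be up to 30 × 2 = 60 gloved imaging sessions, but the number of people would not rise. The up to 10 rehearsal-only volunteers are left out, because the material of the rehearsal gloves is not stated.

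**The case against.** The strongest reply is that glove material is a supply detail. Asking about latex before gloving is ordinary site practice that a protocol need not spell out. An adult who knows of the allergy would probably say so, and staff are present during gowning. This has weight, and it is why the point is minor. It does not remove the point: the protocol does not merely stay silent on a detail, it names the material and requires nobody to ask.

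Four stronger readings are tempting, and the documents do not support them.

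- **That an allergic participant would be exposed.** Disclosure, guided gowning or an unseen Survey 1 item could each prevent it. Only could is justified.
- **That a reaction would end a session after radiation had been given.** Every imaging participant must first complete a rehearsal that includes gowning and involves no radioactivity, and the two visits follow the same steps. If the same gloves are used, an overt reaction or a disclosure may well come at the rehearsal. The exposure concern remains, but the lost-session argument is weak.
- **That the two glove statements contradict each other.** They do not. One is only more specific.
- **That latex is shown to be unnecessary.** The protocol gives no reason for latex, but it does not discuss other materials either. Subjects also hold the loaded e-cigarette, so the gloves may guard against more than exhaled aerosol.

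The consent pages and the gowning pictures are not in the text reviewed, so nothing is concluded from their absence.

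**Conclusion.** The point holds as a minor participant-safety matter. Latex is mandated at the imaging visit, and no eligibility criterion or visit step in the protocol text covers latex allergy. The available medical information cannot be traced to the person being gowned. A latex-allergic participant could therefore be exposed, with the chance reduced but not removed by disclosure, guided gowning and the rehearsal. At most about 0.3 to 1.2 of 30 subjects would be affected, and this rests entirely on the assumed prevalence of 1% to 4%. The finding itself does not depend on that figure. The statistical design is untouched.

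**What to change.** Under Imaging Visit, replace the latex gloves with two sets of non-latex gloves, and use the same wording under Subject Gowning so that the rehearsal is covered too. Because the protocol is silent on which materials suffice, the radiation safety officer should confirm that the chosen glove is adequate for contamination control.

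If the sponsor prefers to keep latex, the written gap can be closed by asking about latex allergy in person at the rehearsal visit, before gowning. Changing the material is simpler, because it needs no further medical information from participants.

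The cost is two wording changes and a supply choice. Eligibility, imaging, dosage, sample size and analysis all stay as they are.

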A maximum of 30 subjects will be included in the imaging portion of this study. Similar to the cold / dress rehearsal volunteers, these participants will complete an initial dress rehearsal visit at the WCIBMI to walk through the study procedures. However, the full study participants will also return to the WCIBMI on a second date to complete the imaging study with the ¹¹C-nicotine ecigarette. Bergstrom et al. (Clinical Pharmacology and Therapeutics, 1995; 57(3):309-17) has reported a relative percent deviation of 34% in the total dose released following 5 minutes of aerosol inhalation (15.4 +/- 5.3%). Assuming an alpha value of 0.05 and a power of 0.8, a sample size of at least 8 subjects is required to observe significant differences in the dose released. One of the aims of this study is to evaluate the next generation PET/CT technology that may exhibit different variance. As a result, larger populations are likely required in order to evaluate a significant difference between the groups. If the power is set to 0.95 to account for this, then the number of subjects required per group is 14. In order to ensure significance and to account for any subjects that do not comply, a total of 30 subjects is requested. Subjects may enroll up to two times (i.e., repeat the imaging study with ¹¹C-nicotine one additional time), but the second enrollment must be at least one week after the first visit.

[figure not shown]

Figure: Schematic of participant procedures. After determined eligible via eligibility surveys, participants will be invited to the WCIBMI to complete the relevant consent forms. If they are participating in the full study, they will first participate in the dress rehearsal, and then study personnel will schedule a time for the participant to return to the WCIBMI and complete the full, imaging portion of the study. If they are participating in only the dress rehearsal, they will not receive any radiation or imaging, and they will receive compensation at the end of the dress rehearsal.

Measurement / Instrumentation

PET/CT imaging will be predominately performed on the next generation digital photon counting PET/CT (Vereos); however, the mobile conventional PET/CT (Gemini TF 64) that is parked on the Martha Morehouse facility will serve as a backup PET/CT imaging system in case of any technical reasons. Our main focus is to utilize the digital PET system, but we need and want the

Version: December 20, 2017 Page 5 of 16

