¹¹C-labeled S-nicotine will be produced at the Kinnear Road facility following a gas-phase method developed by the WCIBMI team (Gosh A. et al, Applied Radiation & Isotopes, 2017, submitted) according to applicable production guidelines for inhalants. In short, purified ¹¹C-labeled S-nicotine will be diluted with the e liquid. The ¹¹C-labeled S-nicotine concentration, radiochemical purity, and specific activity will be determined. Appropriate amount of the e liquid containing ¹¹C-labeled nicotine will be loaded in the e-cigarette cartridge. The radioactivity in the cartridge will be determined, and the e-cigarette will be placed in a lead syringe holder, which will be delivered to the WCIBMI imaging facility at Kenny Road.

¹¹C Dose

The total radioactivity in the cartridge of the e-cigarette will not exceed 9 mCi delivered to the patient. Initially, we will use a dosage of 3 mCi (Dose level A); however, if this dosage does not produce adequate image quality, the dosage will be raised to 9 mCi (Dose level B) for subsequent participants. The release of radioactivity is expected to be 15 +/- 5% during the inhalation phase (Bergstrom et al, Clinical Pharmacology and Therapeutics, 1995; 57(3):309-17). The total delivered dose to the subject will be determined and recorded.

Data Analysis

All PET images will be reconstructed to generate quantitative images for absolute determination of radioactivity distribution. Corrections for the decay of ¹¹C will be applied. The deposition will be shown in 3D and co-localized relative to the anatomy (as provided by the CT images). The total radioactivity will be determined in the head/neck and thorax (e.g., brain, oral cavity, trachea, esophagus, bronchi, lungs, and other relevant soft tissues like muscle). Analysis of other tissues within the imaging field of view may be performed if ¹¹C activity is observed.

The biodistribution, uptake, and clearance will be evaluated in the specified tissues. The results obtained using conventional PET/CT will be compared to the results obtained using the new digital technology. The percent variance in the total radioactivity will be determined at each time point for each tissue.

We are not performing intra-individual comparator examinations. We are focusing on assessing the new generation digital technology and have comparable historical benchmark data available for comparison.

Compensation

Each subject who participates will be eligible for compensation.

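### Between-person tissue results are summarised as absolute radioactivity, which mixes distribution with activity drawn, and the protocol contradicts itself on how the dose that would separate them is measured

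*Protocol*

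**What the plan says.** Data Analysis reconstructs the images for absolute quantification, corrects for decay, totals the radioactivity in each tissue, and then states: "The percent variance in the total radioactivity will be determined at each time point for each tissue". It plans to compare conventional with digital PET/CT results and refers to historical benchmark data. It also says: "We are not performing intra-individual comparator examinations".

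The dose enters as a record only. Under ¹¹C Dose: "The total delivered dose to the subject will be determined and recorded". No section divides tissue activity by it.

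Two features make intake vary between people:
- **Release.** The sample-size paragraph cites a "relative percent deviation of 34% in the total dose released following 5 minutes of" aerosol inhalation, given as 15.4 +/- 5.3%.
- **Loaded activity.** If 3 mCi gives inadequate images, "the dosage will be raised to 9 mCi (Dose level B) for subsequent participants".

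The dose is described in three places:
- **Measurement / Instrumentation** reads the residual in a well counter and defines delivered dose as activity before vaping minus decay-corrected residual. Subjects exhale freely.
- **Imaging Visit** reads the residual in a dose calibrator, after a second pre-vaping check in the imaging facility's dose calibrator.
- **¹¹C Labeling** has an earlier pre-vaping reading at the production site: "The radioactivity in the cartridge will be determined".

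**The concern.** Aim 1 is to establish the biodistribution method, and Aim 2 asks how nicotine distributes. On the stated scale, two people with the same distribution differ in every tissue if one drew more activity from the device. A spread or a scanner difference on that scale cannot be read as a property of distribution or of the scanner. Percent variance is not defined. It could mean spread between subjects or a difference between systems, but intake enters either way.

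Dividing by each person's dose is the natural remedy, and the protocol collects what is needed. But two sections name different instruments for the same residual reading, and the formula does not say which pre-vaping reading applies. The quantity it yields is what left the device, including what was exhaled, so it is an emitted dose and not a retained one.

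**Working it through.** **The protocol's own figure.** CV of release = 5.3/15.4 = 34.4%, matching the stated 34%.

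**One loaded activity.** Take tissue activity = load × released share × tissue share per emitted dose, with the two shares assumed independent. With r the CV of the tissue share (assumed), the CV on the absolute scale is sqrt((1 + r²)(1 + 0.344²) − 1):

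| r | CV on absolute scale |
|---|---|
| 0 | 34% |
| 10% | 36% |
| 20% | 40% |
| 30% | 47% |
| 40% | 55% |

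**Both loads combined.** This applies only if some summary combines them. With share p of subjects at 9 mCi (assumed), the load CV is d = 6·sqrt(p(1 − p))/(3 + 6p). With identical distribution the total CV is sqrt((1 + d²)(1 + 0.344²) − 1):

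| p | d | total CV |
|---|---|---|
| 0.10 | 0.50 | 63% |
| 0.25 | 0.577 | 70% |
| 0.50 | 0.50 | 63% |
| 0.75 | 0.346 | 50% |
| 0.90 | 0.214 | 41% |

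**Scanner comparison.** The conventional system "will serve as a backup PET/CT imaging system in case of any technical reasons", so few scans may fall on it. If k of 30 do (assumed, one scan per subject), release alone gives the difference a standard error of 0.344 × sqrt(1/k + 1/(30 − k)), as a fraction of the mean. This is 35%, 21% or 17% at k = 1, 3 or 5.

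**Sensitivity of the emitted dose.** With released share f, the residual is 1 − f of the load. A relative error b in the residual shifts the emitted dose by b(1 − f)/f. The multiplier is 84.6/15.4 = 5.49 at the mean, 89.9/10.1 = 8.90 at −1 SD and 79.3/20.7 = 3.83 at +1 SD.
- A 1% instrument gap (assumed) gives 5.5%, with range 8.9% to 3.8%.
- A 1-minute reference-time mismatch (assumed), with the protocol's half-life of 20.3 min, is 2^(1/20.3) − 1 = 3.47%. This gives 19%, with range 31% to 13%.

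**Does such a mismatch defeat scaling?** I simulated 2,000,000 draws of lognormal release with identical distribution. Spread is half the 16th-84th percentile range over the median. Raw spread is 34%. After scaling:
- 1% instrument gap: about 2% if it affects everyone, 3 to 4% if it affects a random half.
- 1-minute mismatch: about 6 to 11% if it affects everyone, 10 to 16% if it affects a random half.

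**Random error in both readings (assumed size).** Spread by r in the same simulation, with lognormal tissue share:

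| r | raw | 1% error | 3% error | 4% error |
|---|---|---|---|---|
| 10% | 35% | 14% | 31% | 42% |
| 20% | 40% | 22% | 36% | 46% |
| 30% | 46% | 31% | 44% | 53% |
| 40% | 53% | 41% | 52% | 60% |

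Scaling stops helping between about 3% and 3.5% error per reading.

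**The case against.** **The choice of denominator is detail for an analysis plan.** Absolute quantification describes image reconstruction, totalling radioactivity is a measurement, the dose is recorded, and Internal Validity promises standard procedures and semi-quantitative analysis. Part of this stands: later scaling is not excluded. But Data Analysis names the quantity to be summarised, and the semi-quantitative analysis names no dose scale. An analysis plan would not normally settle a conflict between two procedures.

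**The main outputs survive.** This stands for within-scan results. Regional shares and curve shapes do not depend on intake, nor does the lowest-dose work, for which "PET data will be acquired in listmode and subsequently used for simulation". A reader might infer that Aims 2 and 3 are undermined as a whole; the protocol does not support that.

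**Nothing says the dose levels will be pooled.** This stands. Methods Overview calls them two groups, so the 41 to 70% is conditional.

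**A mismatch in readings mainly moves the level.** This stands. A reader might infer that a mixed instrument or reference time would cancel the benefit of scaling. The simulation shows otherwise at the assumed sizes: 2 to 16% spread against 34% raw. The level shift still matters for the historical comparison.

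**The production-site section names no instrument for the residual.** This stands. The contradiction is between Measurement / Instrumentation and Imaging Visit only; ¹¹C Labeling adds a second candidate pre-vaping reading. Nor can a decay factor be drawn from the 15 minutes under Imaging Visit, which times the positioning of the subject during transport and not the production reading.

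**Conclusion.** The point holds for between-person summaries and for the scanner and historical comparisons. Followed as written, these carry a 34% CV from release alone, on the protocol's own figure. The 36 to 55% range rests on assumed tissue CVs of 10 to 40% that are independent of release. The 41 to 70% range rests on combining dose levels, which the protocol does not say it will do.

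The well counter and the dose calibrator are a direct contradiction, and the formula leaves its pre-vaping reading open. The sizes of 5.5% and 19% rest on an assumed 1% gap and an assumed 1-minute mismatch. They are chiefly a bias in the level of the scaled result, with a modest addition to spread. The change should be made, but the defect does not invalidate the study.

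**What to change.** - For between-person summaries and comparisons, report each tissue and time point in three ways: as a percentage of that subject's emitted dose, as a share of total in-field activity, and as absolute activity. Define percent variance on the scaled values, and say whether it is a spread between subjects or a difference between systems.
- Define emitted dose as device activity before vaping minus residual, both decay-corrected to the start of vaping. State that it includes exhaled activity.
- Reconcile Measurement / Instrumentation with Imaging Visit so that both readings come from the same instrument, and state which pre-vaping reading enters the formula.
- Put the historical benchmark data on the same scale where possible.

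The cost is wording, since both device readings and the PET activity are already collected. Three limits should be stated. The exhaled share remains in the emitted-dose scale. Reading error enters its denominator, so it helps only while random error stays below about 3 to 3.5% per reading; this is why absolute activity is kept alongside. The in-field share needs no device reading, but acquisition begins before the e-cigarette enters the field, so its denominator should count body regions only; it also changes as activity leaves the field.
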